##### 3.2.1. Rationale

Patients with IR and cerebrovascular disease make it difficult to tease out the timing and interactions between IR, poor perfusion and neurodegenerative disease (12, 14, 21, 55). Using an OGTT as a “stress test” for the brain, may evoke acute reductions in perfusion and elevations in ROS, consistent with the concept that a disrupted insulin response directly and indirectly promotes neurocognitive decline, as OGTT.

### 3.2.2. Preliminary Data

First, total CBF is remarkably similar between groups (PC VIPR). However, adolescents with high IR exhibit reduced basal microvascular CP in numerous brain regions, including those involved in cognitive processing (ASL). The combination of MRI approaches suggests an uncoupling of macro and microvascular flow (17) (34), consistent with early but subtle *basal* microvascular dysfunction in IR. Therefore, it is crucial to look at both CBF and CP measures, as regional regulation appears to be differently affected by IR.

Second, following OGTT, regional CBF and CP patterns change markedly. Despite similar increases in plasma glucose, insulin increases much more in adolescents with high IR. CBF through the Middle Cerebral Artery (MCA) increases in adolescents with low IR but *decreases* in adolescents with high IR. Similar patterns were observed in the Anterior Cerebral Artery (ACA, not shown). Third, 45 minutes into OGTT, select regions increased CP in adolescents with low IR, but *decreased* CP in adolescents with high IR. Notably, many of these regions are downstream of the MCA and ACA and are linked with executive function, memory, and learning abilities. These data strongly support the hypothesis that adolescents with high IR demonstrate overt brain endothelial dysfunction, which decreases brain perfusion under the physiologic stress of hyperinsulinemia and hyperglycemia.

In summary, the combination of PC VIPR and ASL MRI approaches allow us to quantify dynamic CBF/CP responses, identify brain regions most sensitive to insulin vasodilation, and most impacted by IR. Preliminary data for Aim 2 OGTT evokes hypoperfusion occurring primarily in anterior brain regions associated with executive function and memory. In the context of insulin-driven ROS production (20, 21), and lower cognition scores (Aim 1), these data are consistent with the hypothesis that acute brain hypoperfusion, via daily insulin surges, plays an essential role in the early pathology of cognitive dysfunction in adolescents with high IR.

## 3.3. Aim 3

To test the hypothesis that higher IR is associated with lower cognitive function (Aim 1) in such a way that perfusion at rest (Aim 2A), and perfusion changes during insulin surge in particular (Aim 2B), mediate the relationship.

### 3.3.1. Rationale

Lower CBF is linked to cognitive decline. OGTT actively reduces CBF/CP in adolescents with high IR, activates ROS (20, 21). These multiple daily insults may independently or collectively contribute to poor cognitive outcomes during this vital stage of brain development.

## 3.4. Study Duration

Expected start date: July 1, 2019

Expected end date: June 30, 2021

#### 4. RESEARCH DESIGN AND METHODS

The procedures described herein are largely the same or similar as that of past procedures outlined in IRB 2014-0529. General procedures that are the same include:

- Pediatric population (healthy and with IR)
- Venipuncture, IV placement, and blood draws
- Cognitive testing
- MRI scans
- OGTT administration

Procedures that differ include:

- Some changes in inclusion and exclusion criteria
- Addition of DEXA scan
- Addition of maximal exercise test
- More extensive cognitive tests

##### 4.1. Subject Population

Fifty-five (55) otherwise healthy adolescents, post-puberty, between 12-18 years of age inclusive.

###### 4.1.1. Inclusion Criteria

Subjects will be included if they meet all of the following criteria:

- Age 12-18 years inclusive
- Typically developing and cognitively intact

We do not plan to recruit subjects at specific levels of IR. By the variable clinical nature of IR, subjects may display similar glucose levels yet a broad range of insulin values. Subjects will have IR quantified directly via the OGTT. The range of IR increases clinical external validity and will provide important pilot data for future studies.

###### 4.1.2. Exclusion Criteria

Subjects will be excluded if they meet any of the following criteria:

- Diabetes ( $\geq 126$  mg dL $^{-1}$  fasting glucose)
- Insulin treatment or sensitizing drugs
- Diagnosis of kidney, pulmonary, or heart disease
  - Note: Subjects with asthma who are taking or prescribed a daily inhaler medication (i.e., daily controller medication) will be excluded. Subjects with only as-needed albuterol prescriptions will not be excluded unless their asthma limits their ability to exercise or they require albuterol prior to any exercise.
- Current smoking\*
- Pregnancy
- Neurological or developmental disorders (e.g., intellectual disability, autism)
- Significant head injury or medical conditions (e.g., concussion, encephalopathy, seizure disorder)
- Inability to undergo the MRI procedure
- Weight less than 94.5 lbs (42.9 kg) to adhere to safety guidelines regarding blood sampling and OGTT administration
- Tanner Stage <3

- Any other circumstance deemed by the PI not addressed above

\*Current smoking will be defined as the use of tobacco or nicotine products >5 times in the past 30 days.

#### **4.1.3. Subject Identification and Recruitment**

Subjects will be recruited primarily from pediatric and pediatric endocrinology clinics via our collaborator, [name], and his staff in UWHC Pediatric Endocrinology. Additionally, subjects will be recruited from the greater Madison, WI community. Subjects may also be recruited from other studies in which our collaborating physician is an investigator:

- 2011-0214
- 2013-1647
- 2015-1172
- 2018-0974

These study consent forms included an authorization to be contacted for future research. Only subjects who signed the authorization will be contacted.

The following methods may also be used for recruitment:

- Mass email to UW-Madison students and staff
- Recruitment flyers
  - Locations may include:
    - UW-Madison campus and UW Hospital buildings
    - Local middle schools and high schools
      - Middleton/Cross Plains School District
      - Verona School District
      - Sun Prairie School District
    - Local businesses
    - Local physician offices
- Website postings (e.g. Craigslist, UW Student Job Center)

All recruitment material used will be IRB approved prior to posting.

Enrollment will continue until the target sample size (see section [4.1 Subject Population](#)) completes all study procedures.

#### **4.2. Research Sites**

The following sites will be used for the following purposes:

- UW Medical Sciences Building
  - Maximal exercise testing
- UW Human Exercise Research Core (HERC) in the UW Nursing School\*
  - Maximal exercise testing
  - DEXA Scan
- Clinical Research Unit (CRU)\*
  - Screening visit blood draw
- Wisconsin Institute of Medical Research (WIMR)
  - MRI

- IV placement
- Waisman Center
  - MRI
  - IV Placement
- UW Hospital
  - Cognitive testing

\*This flexibility is requested to prevent potential space usage conflicts in the UW Natatorium. Firstly, other currently approved research in the PI's laboratory utilizes the limited space at the UW Natatorium. Secondly, in anticipation of the closing of the UW Natatorium circa summer 2020 and subsequent laboratory transition to the Medical Sciences Building. Thus, having the ability to conduct the necessary research at the UW HERC in the Nursing School or the CRU will allow the proposed research project to continue with minimal interference.

### 4.3. Experimental Procedures

#### 4.3.1. Pre-Screening Subjects

Delegated study team members will screen patients for eligibility for the study based on medical history, medication use and evaluate general safety to undergo MRI (e.g. claustrophobia, metallic implants, etc.). Consent/permission will be obtained following a description of the study and prior to survey questions either:

- verbally for phone screen
- agreeing to the REDCap survey

The same script/information sheet will be used for both the phone screening and REDCap survey (i.e. the REDCap survey will be discussed with the subject verbally and constitutes the “phone screen”).

Medical records of potential subjects will be reviewed by staff under the supervision of [name] from [name] clinic(s) for fasting glucose and insulin to determine subject's eligibility for the study. This review will occur prior to pre-screening procedures.

These steps will be taken to minimize risk of participation. If an individual does not preliminarily meet all inclusion criteria or preliminarily meets any of the exclusion criteria, then the subject will be immediately eliminated from consideration for the study and their information will be destroyed (e.g. shredder or digital deletion).

#### 4.3.2. Screening Subjects

Screening will be split into two (2) parts:

- Part 1 (virtual): Approximately 1 hour
- Part 2 (in-person): Approximately 0.5-1 hour

##### 4.3.2.a. Virtual Screening Procedures

Procedures include:

- e-Consent:
  - Subjects and subject's parent(s) (if subject <18 years) will first be contacted regarding their preliminary eligibility and attainment of parental permission (if applicable). A REDCap link to the electronic version of the Informed Consent form and Informed Assent form (if

applicable) will be sent to the subject and subject's parent(s) (if applicable). Electronic verification and signature/initials will be obtained prior to other study activities.

- Questionnaires
  - Following attainment of consent, subjects and subject's parents (as applicable) will complete the following questionnaires in a virtual format via REDCap:
    - Health history (via questionnaire)
    - MRI safety (via questionnaire)

For participants <18 years old, the pre-screening survey answers will be reviewed with the parent of the potential subject to ensure accuracy. Any discrepancies will be documented. Verbal verification of accuracy by the parent will be documented.

#### 4.3.2.b. In-Person Screening Procedures

A visit reminder will be provided to potential subjects via phone or email at least 24 hours prior reminding them of the following (see Sections [4.2. Research Sites](#) and [4.3.4.b. Fasting, and Caffeine, NSAID and Exercise Restriction](#)):

- Location of visit (with general campus directions)
- Fasting directions
- Caffeine, NSAIDs, and exercise restriction
- Inform the study team if any albuterol, inhaled steroids, or systemic steroids were taken within 48 hours

Subjects will arrive fasted.

The subject will be screened in-person for the following:

- Pregnancy\*
- Height and weight
- Hip and waist circumference
- Blood draw
- Body composition via DEXA†
- Maximal exercise test†

\*Female subjects will be asked whether they might be pregnant in a private setting away from their parents, and the information will not be shared with their parents.

†For scheduling reasons and the fact that the data obtained from these procedures do not affect eligibility, the DEXA scan and the maximal exercise test can be performed on any of the study visits or on independent visits.

The results of the screening procedure will be valid for study inclusion for 180 days. If the subject does not complete all study visits within 180 days of screening, another screening procedure will take place.

Other studies in the PI's lab that investigate the same subject population collect similar screening data and utilize many of the same procedures. To reduce subject burden, we will use all applicable screening data from the other study's screening procedure and perform only those procedures that were not previously performed. The use of previous data will be documented. The results of the screening procedure will be valid for study inclusion for 180 days from date of collection. If the subject does not complete all study visits within 180 days of screening, another screening procedure will take place.

### 4.3.3. Study Visits

Duration: Approximately 6.5-8 hours total.

The study involves 2-3 visits to the WIMR, Waisman Center, or UW Hospital (see section [4.2 Research Sites](#)). Because the data collected in each visit is not dependent on the other visit in a temporal manner, the study visits can occur in any order (i.e. one visit does not need to occur before another). Additionally, the flexibility of conducting study visits in any order allows enhanced scheduling opportunities for subjects and staff.

The “Cognitive Testing” and “MRI Structural Scanning” study visits (see section [4.3.3.a Cognitive Testing Visit](#) and [4.3.3.b MRI Structural Scanning Visit](#)) may occur together or independently as best suited for the subject and research staff. This flexibility allows the potential for the reduction in the number of study visits or the reduction in the time spent at a single visit.

A visit reminder will be provided to potential subjects via phone or email at least 24 hours prior reminding them of the following (see Sections [4.2. Research Sites](#) and [4.3.4.b. Fasting, and Caffeine, NSAID and Exercise Restriction](#)):

- Location of visit (with general campus directions)
- Fasting directions
- Caffeine, NSAIDs, and exercise restriction

Subjects will arrive fasted prior to study visits. Parent(s)/guardian(s) will be encouraged but not required to be present during the study visits (exception: cognitive testing visit).

#### 4.3.3.a. Cognitive Testing Visit

Duration: Approximately 2-3 hours.

Subjects will arrive fasted.

Subjects will undergo formal neuropsychological evaluations led by collaborators Drs. [name] and [name] and administered by trained personnel. Selected tests (see section [4.3.4.e. Cognitive Tests](#)) reflect a broad set of core cognitive domains and related tests, which retain the same item pool across the age range to be investigated to facilitate examination of factors that influence cognitive development in youth with IR (25, 40, 41, 46, 47). This comprehensive approach aims to maximize our ability to detect and interpret subtle functional changes.

There is potential for confounders, such as history of academic problems, depression, ADHD, or anxiety. These factors will be assessed through a structured interview with the child’s parent(s)/guardian(s) by an interviewer blinded to all cognitive and psychiatric information, and will assist in interpreting cognitive results. No cognitive information about the parent(s)/guardian(s) will be obtained; they will solely act as informants.

#### 4.3.3.b. MRI Structural Scanning Visit

Duration: Approximately 1 hour.

Subjects will arrive fasted.

We do not expect differences in brain structure (but will compare statistically), but comprehensive imaging will examine potential neuroanatomical differences, and control for brain volume differences between subjects. Subjects will lie supine for approximately 1 hour while various MRI neuroanatomical, CBF, and CP scans are performed. Scans may include T1-weighted imaging, Diffusion Tensor Imaging, T2, T2FLAIR, MPnRAGE, ASL, and PC VIPR. These scans are well-established methods used by the PI's collaborators in the Wisconsin Alzheimer's Disease Research Center (4, 17, 43, 44).

#### 4.3.3.c. OGTT and MRI Scanning Visit

Duration: Approximately 2 hours.

Subjects will arrive fasted.

Subjects will have one (1) IV catheter placed (see section [4.3.4.i. Intravenous Catheter](#) for details) and then lie supine in the MRI machine. Subjects undergo baseline MRI scans lasting approximately 20 minutes, following which subjects will be removed from the MRI bore to sit to drink 75g glucose (OGTT; see section [4.3.4.g. Oral Glucose Tolerance Test \(OGTT\)](#) for details) within 5 minutes followed by return to MRI bore. Finally, paired MRI scans (PC VIPR and ASL) will be repeated over the next 60 min, with IV blood sampling to quantify insulin and glucose changes. MRI scan time will end approximately 60 min post-OGTT:

[figure not shown]
- 1) for subject comfort in MRI
- 2) as pilot studies indicate robust perfusion changes occur within 60 minutes

ASL scans will be taken at the following time points (note times are approximate due to variance in scan times):

- Baseline (pre-OGTT)
- 10 minutes after OGTT
- 25 minutes after OGTT
- 40 minutes after OGTT
- 55 minutes after OGTT

PC VIPR scans will be taken at the following time points (note times are approximate due to variance in scan times):

- Baseline (pre-OGTT)
- 15 minutes after OGTT
- 30 minutes after OGTT
- 45 minutes after OGTT
- 60 minutes after OGTT

#### 4.3.4. Details of Procedures

##### 4.3.4.a. Informed Consent/Assent

Informed consent/assent will be obtained from each participant outlining the potential risks. Consent/assent will be obtained at the initial screening visit and will take place prior to any other procedures being performed. If written consent/assent is refused, the subject will no longer be considered for the study.

##### 4.3.4.b. Fasting, and Caffeine, NSAID and Exercise Restriction

Each subject will be asked to:

- fast for a minimum of 4 hours
- refrain from using NSAIDs (e.g. Ibuprofen) for a minimum of 24 hours
- refrain from caffeine for a minimum of 24 hours
- refrain from vigorous exercise for a minimum of 24 hours
- inform the study team if any albuterol, inhaled steroids, or systemic steroids were taken within 48 hours

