#### **4.3.4.h. Oral Glucose Tolerance Test (OGTT)**

OGTTs are clinically safe and a minimally invasive procedure to quantify IR. After a minimum 4-hour fast, subjects consume, within 5 min, a beverage containing 75 grams glucose (similar to a can of soda). This is the standard administration of OGTT (Poomthavorn, Nantarakchaikul, Mahachoklertwattana, Chailurkit, & Khlairit, 2013). Blood sampling occurs for 60 minutes (see section [4.3.4.j Blood Sampling](#)). The [name] lab has conducted multiple OGTT studies in IR adults and found the OGTT with MRI measures is well tolerated.

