### 7.10.2 Subject Stopping Guidelines

Each intervention (i.e. study visit) will be terminated based on the following specific guidelines:

- If the subject wishes to stop
- If the subject complains of serious pain or discomfort
- If the subject is admitted to hospital for psychiatric distress
- If the subject complains of (related to MRI):
  - Discomfort
  - Anxiety
  - Claustrophobia
- If baseline glucose is  $\geq 126$  mg/dL and is not the result of non-compliance with fasting requirement (see [4.1.2. Exclusion Criteria](#))
- Any SAE occurring during study procedures

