## 8. STATISTICAL CONSIDERATIONS

Covariates for all analyses include sex, age, adiposity, aerobic fitness, and education unless noted otherwise.

The overarching statistical approach uses multiple regression to determine whether IR is inversely associated with outcome measures in Aims 1 and 2 and to assess mediation in Aim 3. Mean/summed outcomes (total cognition, total CBF or CP) will be predicted by HOMA-IR, for example. Not only is a composite measure calculated as a mean more reliable than the subdomain scores, but averaging multiple measures of a single construct yields a more powerful hypothesis test than using variables individually (40), under conditions we expect to hold here. This approach avoids inflation of Type I error rate as each hypothesis test examines the relationship among single variables or composites, not among multiple subdomain measures. If the test of the mean or composite score is significant, then there is no increased Type I error rate incurred in subsequent subdomain/regional tests (41).

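### HOMA-IR predicts the outcome in every aim, but the blood behind it needs only a 4-hour minimum fast at no set time of day, and no model adjusts for either

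*Combined protocol and SAP*

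**What the plan says.** Section 4.3.4.b asks each subject to "fast for a minimum of 4 hours". Section 4.3.4.h repeats the rule for the glucose test: "After a minimum 4-hour fast, subjects consume, within 5 min, a beverage containing 75 grams glucose". The screening visit falls under it too: Section 4.3.2.b states "Subjects will arrive fasted", and its visit reminder cross-refers to 4.3.4.b. No section asks for an overnight fast, caps the fast or fixes a start time. On scheduling, Section 4.3.3 says that "the flexibility of conducting study visits in any order allows enhanced scheduling opportunities for subjects and staff".

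Section 8 gives the general approach: "Mean/summed outcomes (total cognition, total CBF or CP) will be predicted by HOMA-IR, for example". Sections 8.2, 8.3.2, 8.3.3 and 8.4 then use HOMA-IR in Aims 1, 2A, 2B and 3. The common covariates are sex, age, adiposity, aerobic fitness and education, with intracranial volume added for the conductance (CVC) analyses.

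The 126 mg/dL exclusion in Section 4.1.2 is labelled "fasting glucose". Section 7.10.2 applies the same figure to baseline glucose at a visit, provided that it "is not the result of non-compliance with fasting requirement". For clinic recruits, Section 4.3.1 also has charts reviewed "for fasting glucose and insulin to determine subject's eligibility for the study", with no fast length given.

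**The concern.** The study relates one measured exposure to cognition and perfusion, so the conditions under which that exposure is measured matter to every result. Under the rule as written, a subject sampled in the afternoon 4 hours after lunch and a subject sampled in the morning after a night's fast are both compliant. HOMA-IR is usually computed from one fasting glucose and one fasting insulin value (the documents give no formula, so this is an assumption). The two subjects' values would then be taken under different conditions, and no model would account for it.

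The outcome may be touched as well. If the baseline sample of the OGTT-MRI visit supplies HOMA-IR, the same differences in recent intake bear on resting CVC (Aim 2A) and on the baseline from which ΔCVC is measured (Aim 2B). Exposure and outcome would then share a source of variation.

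The plan has little to catch this. Section 7.9 places the insulin assays towards the end of the study. Section 10 accepts any three of the seven draws at the OGTT-MRI visit, so the baseline draw is not required. Sections 4.3.2.b and 7.9.1 allow screening data from the laboratory's other studies, without saying that their fasting rule was the same.

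**Working it through.** **1. What following the plan exactly allows.** Minimum fast: 4 hours (4.3.4.b, 4.3.4.h; 4.3.2.b by cross-reference). Maximum: none. Clock time: none. Adjustment: none (Section 8 covariates). An unstandardised exposure is therefore compliant.

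**2. Which sample supplies HOMA-IR.** Blood is drawn at screening and at the OGTT-MRI visit (4.3.4.k). Section 4.1.1 says that IR is quantified through the OGTT, while Section 8 uses HOMA-IR; no section names the sample. The 4-hour rule covers both.

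**3. Reproducing the plan's sample size.** Inputs from 8.3.2: r = −0.324, one-tailed α = 0.05, power 0.80, N = 55. One-tailed noncentral-t test of a correlation, using |r|:

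- df = N − 2 = 53, critical t = 1.674
- noncentrality = r√N / √(1 − r²) = 0.324 × 7.416 / 0.946 = 2.54
- power = 0.806, and N = 55 is the smallest N that reaches 0.80

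The same method gives the plan's other figures exactly: 13 (r = 0.6), 31 (0.42), 6 (0.796), 41 (0.37) and 34 (0.4). The plan's arithmetic is sound. Aim 2A sets the sample size and has almost no spare power.

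**4. Illustration of random error in HOMA-IR.** The documents give no reliability for HOMA-IR after a 4-hour fast, so R below is assumed. Further assumptions: the error is random and unrelated to true insulin resistance, and the pilot correlations are free of it. Then r(observed) = r√R. For Aim 2A with R = 0.7: 0.324 × √0.7 = 0.271, and noncentrality = 0.271 × 7.416 / 0.963 = 2.09.

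| Assumed R | Aim 2A r | Power at N=55 | N for 0.80 | Aim 2B (micro, r = 0.42) power | Aim 1 (r = 0.6) power |
|---|---|---|---|---|---|
| 1.0 | 0.324 | 0.806 | 55 | 0.959 | 1.000 |
| 0.9 | 0.307 | 0.764 | 61 | 0.938 | 1.000 |
| 0.8 | 0.290 | 0.716 | 69 | 0.907 | 0.999 |
| 0.7 | 0.271 | 0.662 | 80 | 0.865 | 0.995 |

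The loss falls mainly on Aim 2A. The Aim 3 power figures in 8.4 concern the path from CVC to cognition, where HOMA-IR is not the tested predictor, so this calculation does not apply to them.

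**5. The fasting label on the glucose criterion.** Section 4.1.2 calls 126 mg/dL a fasting value. Section 7.10.2 recognises that recent food can raise baseline glucose, but makes an exception only for a breach of the fasting requirement. A sample taken 4 hours after a meal meets that requirement and so counts as fasting.

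**The case against.** **Four hours is a floor.** Many subjects may fast longer, and no document gives actual fasting times. This stands: a reader might infer that some HOMA-IR values are in fact post-meal, but the text supports only that they may be.

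**The pilot may already carry the error.** Section 4 describes procedures as largely the same as in the earlier study, lists OGTT administration among those that are unchanged, and does not list fasting among the differences. If the pilot used this rule, subtracting a further loss from its correlations counts the error twice. The documents do not state the pilot's fast, so this stands as a serious limit on the power illustration.

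**The direction of bias is open.** A reader might infer that the association is pulled towards zero. That follows only for random error. Section 3.2.2 reports that insulin rose much more in high-IR pilot subjects after the glucose load. If leftover insulin also rises with IR, the error tracks the exposure, may largely preserve the ranking of subjects, and could bias the result in either direction.

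**A tempting stronger reading of the size.** The pilot means were about 3.4 and 4.6, and 4.6/3.4 = 1.35, so a 35% rise would carry a low-IR subject to the high-IR mean. The arithmetic is right, but no document gives a post-meal elevation of that or any other size at 4 hours.

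**Staff may record fasting times anyway.** The visit checklists and CRFs are not in the documents, and the exception in 7.10.2 implies some check on fasting. So the claim must be that the protocol does not state such recording, not that none takes place.

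**The glucose criterion is applied consistently.** Sections 4.1.2, 4.3.4.b and 7.10.2 can be read as using one fasting definition throughout. That is a fair reading. What remains is a label to be reconciled, not a demonstrated contradiction.

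**Conclusion.** The concern holds as a gap in standardisation: the predictor in every aim is measured under conditions that the plan leaves free and does not adjust for. The error is avoidable, but its size and direction are not established by the documents. Aim 2A is the most exposed because it has no power to spare. The range of 0.76 to 0.66 against 0.81 rests on random error, error-free pilot correlations and an assumed reliability of 0.9 to 0.7. It is an illustration, not an estimate of what the study will lose.

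The documents do not support a reading that the exposure is invalid or that the study must stop until this is changed. It is a cheap improvement that should be made, and early, because intake times that were never written down may not be recoverable.

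**What to change.** 1. Record time of last caloric intake and clock time at the screening draw and at the OGTT-MRI visit.
2. Name the sample that supplies HOMA-IR and state the formula. Require that sample for a valid exposure, in addition to the rule of three draws out of seven in Section 10.
3. Add hours since intake and clock time as covariates in the HOMA-IR models where they are available, with a sensitivity analysis limited to samples taken after an overnight fast.
4. For future subjects, set one uniform fasting window and one start-time window for the visit that supplies HOMA-IR. The length and timing are for the sponsor to decide.
5. Separately, reconcile the fasting label on the 126 mg/dL criterion (4.1.2, 7.10.2) with the fasting requirement in 4.3.4.b. No threshold or clinical rule is proposed here.

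Cost: protocol and reminder wording, one added CRF field, up to two model degrees of freedom, less flexible scheduling and possibly longer fasts for some subjects. For subjects already sampled, the times may be missing, so the adjusted and restricted analyses may cover only part of the sample.
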